2.3 PHARMACOKINETIC ENDPOINTS

In Stage 1, the individual plasma concentration-time data following intravenous infusion of rhPTX-2 will be analyzed to obtain the following pharmacokinetic (PK) parameters, where applicable:

- C_{max} (maximum observed plasma concentration)
- t_{max} (time at which the maximum plasma concentration was observed)
- AUC_{0-last} (area under the plasma concentration-time curve from time 0 to time of last measurable plasma concentration)
- AUC_{0-∞} (area under the plasma concentration-time curve from 0-time extrapolated to infinity)
- t_{1/2} (apparent terminal elimination half-life)
- CL (clearance)
- Vd (volume of distribution)

The PK endpoint for Stage 2 subjects is the total PTX-2 level prior to drug administration at the pre-defined timepoints (see Appendix 5 and Appendix 6 Schedule of Assessment). Samples for rhPTX-2 PK analysis were not collected in Stage 2.

2.4 SAFETY OUTCOME MEASURES

Safety parameters to be measured include exposure, adverse events (AE) (including serious adverse events [SAEs], adverse events of special interest [AESI], AE leading to drug discontinuation, and deaths), clinical laboratory results (hematology, chemistry, and anti-drug antibodies), vital signs, electrocardiogram (ECG), and concomitant medication use.

2.5 DETERMINATION OF SAMPLE SIZE

Details regarding the sample size for Stage 1 and Stage 2 are described in the Appendix 1 and Appendix 3 (Protocol Synopsis).

For the OLE, no target sample size was delineated. The sample size was determined by the number of subjects who rollover from the main study. The study was intended to provide access to rhPTX-2 for any subjects in the main study for whom the investigator felt clinical benefit could be realized or extended.

2.6 ANALYSIS TIMING

The full study analysis will be conducted at the completion of the study as defined in the protocol (completion of each stage and OLE). This being an open-label non-inferential study, occasional exploratory analyses may be conducted throughout the study to inform the clinical development plan.

3. STUDY CONDUCT

3.1 RANDOMIZATION

Subjects in Stage 1 were not randomized.

Subjects in Stage 2 were randomized to treatment group with a 1:1:1 randomization ratio. A central randomization system was used. The randomization was stratified according to the subjects' baseline hematologic status: baseline anemia alone (subjects with Hgb < 100 g/L and having received \geq 2 units PRBC in the 12 weeks prior to study entry) or baseline thrombocytopenia (platelet count < 50 x 10^{9} /L) or baseline anemia associated with baseline thrombocytopenia. The randomization system ensured that at least 50% of the subjects in the final study population have baseline thrombocytopenia from the second stratum (platelet count < 50 x 10^{9} /L).

3.2 INDEPENDENT REVIEW FACILITY

For Stage 1 and Stage 2, all bone marrow assessments were performed by a committee of expert hematopathologists, who were blinded to subject, dose, and time of biopsy.

The rules for assessment and adjudication are defined in the Central Bone Marrow Review Committee charter.

3.3 DATA MONITORING COMMITTEE

Stage 1 had no Data Monitoring Committee (DMC) in place.

In Stage 2, a DMC was established for purposes of independent assessment of safety during study conduct.

4. STATISTICAL METHODS

Except where specified, all continuous variables will be summarized by treatment group with descriptive statistics (the number of non-missing values, mean, standard deviation, median, minimum, and maximum). All categorical variables will be summarized with frequency counts and percentages, by treatment group.

4.1 ANALYSIS POPULATIONS

4.1.1 All treated Population

Stage 1:

All subjects who have received at least one dose of rhPTX--2. The primary assessment of all efficacy analyses will be performed on this population.

Stage 2:

The all treated population will consist of subjects:

randomized and, who have received at least one administration of the drug

In the event of subjects, having received treatments that differed from those assigned according to the randomization schedule, then the efficacy analyses will be conducted according to the randomized treatment (As randomized analysis).

This population will be the primary population for the efficacy analyses.

4.1.2 Pharmacokinetic Population

Stage 1:

The PK population includes all subjects who have received at least one dose of rhPTX-2 and have at least one measurable post-dose total PTX-2 concentration result.

The PK evaluable population includes all subjects who completed at least 1 cycle and had sufficient total PTX-2 concentration data to accurately estimate at least one PK parameter in at least 1 cycle.

Stage 2:

The PK population includes all subjects who have received at least one dose of rhPTX-2 and have at least one post-dose total PTX-2 concentration result.

4.1.3 Safety Population

For both stages, the safety population consists of subjects who have received at least one dose of study drug.

For Stage 2, in the event of subjects having received treatments that differed from those assigned according to the randomization schedule, then the safety analyses will be conducted according to the treatment actually received (As Treated Analysis).

4.1.4 Open Label Extension Population

For both stages, the OLE population consists of all subjects who received at least one dose of rhPTX-2 during the OLE phase.

4.1.5 Open Label Extension Subjects with Bone Marrow Biopsy Population

For both stages, the OLE patient populations with BM biopsy consist of all subjects who received at least one dose of rhPTX-2 during the OLE phase and have at least one BM biopsy result available during the OLE.

4.2 ANALYSIS OF STUDY CONDUCT

All analyses will be performed by study stage separately. The number of subjects who are enrolled and/or randomized (Stage 2 only) will be tabulated by treatment group, center and country. Major eligibility exceptions, major protocol deviations and reasons for study discontinuation will be summarized by treatment group for all subjects.

4.3 ANALYSIS OF TREATMENT GROUP COMPARABILITY

Descriptive summaries will be provided for all baseline characteristics. The summaries will be provided for both stages separately. Demographic and baseline variables that will be summarized by treatment group include at least:

- Stratification factors (Stage 2 only):
 - Baseline anemia (Hgb < 100 g/L and having received > 2 units PRBC in 12 weeks prior to study entry) alone
 - Baseline thrombocytopenia (platelet count < 50 x 10⁹ /L) alone
 - Baseline anemia associated with baseline thrombocytopenia
- Demographics for both Stages:
 - Gender
 - Age at consent (continuous and categorical)
 - Race
 - Ethnicity (if available)
 - Weight at baseline

Should country policy prohibit the collection of race and/or age information, subjects will appear in the missing category of summary tables.

- MF history for Stage 1:
 - Number of years since diagnosis
 - Bone marrow fibrosis grade at baseline
 - Spleen size below left costal margin at baseline
 - Type of MF (PMF, post-PV MF or post-ET MF)
 - Risk group with PMF (low, intermediate-1, intermediate-2, or high)
 - Red blood cell transfusion history 3 months prior to first dose
 - Number of subjects transfused (PRBC, Platelets, Fresh frozen plasma)
 - Number of subjects with baseline hemoglobin < 100 g/L at baseline
 - Number of subjects with platelets < 50 g/L and <25 g/L at baseline
 - Number of units of platelet and RBC transfusions
 - Number of subjects previously treated with ruxolitinib
- MF history for Stage 2:
 - Number of years since diagnosis
 - Bone marrow fibrosis grade at baseline
 - Spleen size measured by CT, positron emission tomography-CT (PET-CT) or MRI at baseline
 - Type of MF (PMF, post-PV MF or post-ET MF)
 - Risk group with MF (DIPSS low, intermediate-1, intermediate-2, or high)
 - Number of subjects with at least one transfusion in 12 weeks prior to baseline (RBC and platelet)
 - Number of subjects with baseline hemoglobin < 100 g/L at baseline
 - Number of subjects with platelets < 50 g/L and <25 g/L at baseline
 - Number of units of platelet and RBC transfusions
 - Number of subjects previously treated with ruxolitinib

In addition, for both stages, ruxolitnib history will be presented.

4.4 EFFICACY ANALYSIS

All analyses will be performed separately for each stage.

4.4.1 Primary Efficacy Endpoint

Stage 1:

The ORR will be compared against a fixed level of 10% using one-proportion Z-test.

The hypothesis test will be performed separately in each of the 4 treatment groups and overall, each at the 5% significance level (one-sided; statistical significance will be concluded if the lower bound of the 2-sided 90% CI is above 10%).

Subjects with no post-baseline IWG response assessments will be considered non-responders.

Stage 2:

The BMRR will be described as the percent of subjects with a reduction in bone marrow fibrosis score by at least one grade from baseline to any time of the study.

The BMRR will be presented within each treatment group with the corresponding 95% CI.

The BMRR will be analyzed using a logistic regression with bone marrow response at any time during the study (yes/no) as response variable and treatment group as explanatory variable. The analysis will be adjusted on randomized stratum. Pairwise comparisons between the 3 treatment groups will be performed.

Two pairwise comparisons (3 mg/kg versus 0.3 mg/day and 10 mg/kg versus 0.3 mg/day) will be computed with the aim to demonstrate superiority and therefore, will use an adjusted two-sided level of significance of 0.025. The third comparison (10 mg/kg versus 3 mg/kg) is not expected to have enough power to demonstrate any difference with the planned sample size. This comparison is considered exploratory and will be conducted using an unadjusted two-sided 0.05 level of significance.

The protocol proposed a threshold of 10% as the lower limit for clinically relevant response. For the 3 mg/kg and 10 mg/kg groups, the lower limit of the 97.5% two-sided confidence interval will be compared to this threshold of 10%. If the lower limit of the confidence interval is above 10%, the corresponding dose will be claimed to have demonstrated clinically relevant efficacy.

For subjects with no readable post-baseline BM biopsy results available, the conservative rule to consider them as non-responders will be used.

4.4.2 Secondary Efficacy Endpoints

Stage 1:

For Stage 1, no formal hypothesis testing will be performed for the secondary efficacy endpoints. All summaries will be presented by treatment group and overall.

The bone marrow biopsy results will be analyzed as:

- Myelofibrosis grade shifts relative to baseline at Weeks 12 and 24.
- Myeloblasts and cellularity will be presented at baseline, Weeks 12 and 24 as well as change from baseline
- Collagen grade shifts relative to baseline at Weeks 12 and 24.

The modified MPN-SAF TSS will be presented descriptively at baseline and at the beginning of each cycle (Cycle 2 onward). In addition, the number of subjects with \geq 25% and \geq 50% reduction relative to baseline at the beginning of each cycle (Cycle 2 onward) will be presented.

Stage 2:

Duration of effect of the three doses on reduction in bone marrow fibrosis:

- To assess the duration of effect of the three doses on bone marrow improvement a
 Kaplan-Meier plot will be provided. Duration of BM improvement will be defined for
 responding subjects as time from first decrease from baseline of one grade to time of
 return to baseline levels. If no return to baseline levels then duration will be
 censored at the last BM assessment
- Effect and duration of effect of the three doses on disease related anemia, thrombocytopenia, and constitutional symptoms: For patients with improvement, the duration of improvement is defined as the number of weeks of improvement from the first12 weeks of improvement period.

IWG-MRT response will be summarized by treatment group at each visit by percent of subjects with complete response, partial response, clinical improvement, stable disease and progressive disease according to IWG-MRT criteria.

4.4.3 Exploratory Efficacy Endpoints

The exploratory endpoints will be summarized using tables, listings and graphs as appropriate.

4.4.4 Sensitivity Analyses

For Stage 2, a non-stratified analysis of BMRR will be computing as a sensitivity analysis.

4.4.5 **Subgroup Analyses**

Stage 1:

• Primary endpoint results will be presented by risks groups (intermediate-1, intermediate-2, or high risk subjects).

Stage 2:

- Primary endpoint results will be presented:
 - by risks groups (intermediate-1, intermediate-2, or high risk subjects)
 - for each strata separately (baseline anemia alone, baseline thrombocytopenia alone, baseline anemia and thrombocytopenia)
 - by transfusion status at baseline with transfusion dependency defined as: ≥ 2
 units PRBC every 4 weeks for 12 weeks prior to or after C1D1
 - by PTX-2 level at baseline classify by High/Low category (median as the cutoff)

The platelet improvement analyses will be presented by platelet levels (subjects with platelet <50 x10^9/L at baseline and subjects with platelet <25 x10^9/L at baseline)

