## 5. STAGE 2 SELECTION OF STUDY POPULATION

### 5.1 Study Population

#### 5.1.1. Inclusion Criteria

This Phase 2 study will enroll up to 111 subjects with MF, 27 in Stage 1, and up to an additional 84 subjects in Stage 2

Each subject must meet all of the following inclusion criteria to be enrolled in the study:

1. Subjects must be  $\geq 18$  years of age at the time of signing the Informed Consent Form (ICF);
2. Subjects must voluntarily sign an ICF;
3. Subjects must have a pathologically confirmed diagnosis of PMF as per the WHO diagnostic criteria (see [APPENDIX C](#)) or post ET/PV MF;
4. At least Grade 2 marrow fibrosis according to the WHO Grading of Bone Marrow Fibrosis ([APPENDIX D](#));
5. Intermediate -1, intermediate -2, or high risk disease according to the IWG-MRT Dynamic International Prognostic Scoring System (see [APPENDIX E](#));
6. A bone marrow biopsy must be performed within four weeks prior to Cycle 1 Day 1 treatment to establish the baseline fibrosis score;
7. Subjects must not be candidates for ruxolitinib based on EITHER:
  - a. Platelet count  $< 50 \times 10^9/L$ , OR
  - b. Hgb  $< 100$  g/L have received  $\geq 2$  units PRBC in the 12 weeks prior to study entry, and be intolerant of or had inadequate response to ruxolitinib;
8. Subjects must have an Eastern Cooperative Oncology Group (ECOG) Performance Status of 0-2. ([APPENDIX F](#));
9. Life expectancy of at least twelve months;
10. At least four weeks must have elapsed between the last dose of any MF-directed drug treatments for myelofibrosis (including investigational therapies) and study enrollment;
11. Recovery to  $\leq$  Grade 1 or baseline of any toxicities due to prior systemic treatments, excluding alopecia;

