**Study Design:**

This is an open-label, Simon two stage, Phase 2 study to determine the efficacy and safety of two different dose schedules of PRM-151 in subjects with PMF and post ET/PV MF. There are two treatment cohorts, each assigned to one of two dose schedules of PRM-151. Subjects will be assigned to a weekly or every four week dosing schedule by the investigator based on their ability to visit the study site on a weekly basis. This is an adaptive design as defined in FDA Draft guidance for Industry: Adaptive Design Clinical Trials for Drugs and Biologics, February 2010. Modifications to dose levels, schedule, or regimen may be made in Stage 2 based on data from Stage 1.

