**Stage 1:**

Cohort 1: Approximately 12 subjects with intermediate -1, intermediate -2, or high risk MF who have received no treatment for MF in at least two weeks will be enrolled and assigned to treatment with single agent PRM-151 at a dose of 10 mg/kg IV on Days 1, 3, 5, 8, 15, and 22 of Cycle 1 and Days 1, 8, 15 and 22 of each subsequent 28 day cycle for six cycles, OR single agent PRM-151 at a dose of 10 mg/kg administered IV on Days 1, 3, and 5 of Cycle 1 and Day 1 of each subsequent 28 day cycle for six cycles. Subjects responding to therapy may continue receiving it as long as there is a benefit.

Cohort 2: Approximately 12 subjects with intermediate -1, intermediate -2, or high risk MF on a stable dose of ruxolitinib for at least 12 weeks, with no improvement in spleen during the last four weeks will be enrolled. Subjects will be assigned to receive PRM-151 in combination with ruxolitinib either at a dose of 10 mg/kg administered IV on Days 1, 3, 5, 8, 15, and 22 of Cycle 1 and Days 1, 8, 15 and 22 of each subsequent 28 day cycle for six cycles, OR in combination with ruxolitinib at a dose of 10 mg/kg administered IV on Days 1, 3, 5 of Cycle 1 and Day 1 of each subsequent 28 day cycle for six cycles. Subjects responding to therapy may continue receiving it as long as there is a benefit.

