**Statistical Methods:**

The objective is to demonstrate superiority within each cohort and dose schedule, comparing observed ORR in each arm to a fixed uninteresting level ORR of 0.1. Let  $\pi$  denote population expected value of the primary parameter ORR. The objective of the trial is to reject the null-hypothesis

[figure not shown]

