**$H_0: \pi < 0.1$**

in favor of the alternative hypothesis

$$H_A: \pi > 0.4$$

The design will be two-staged within each arm based on Simon (Simon 1989) as shown in the figure below:

The design maintains the type I error probability at 3.4 % which is less than 5 %. Furthermore, for  $\pi > 0.4$ , there is a high probability of at least 94 % to demonstrate superiority. The probability under  $H_0$  to stop after stage 1 is 53 %, which implicit consequence that the expected number of subjects is 15, compared to a maximum number of subjects of 26.

**Date of Original Protocol:** Version 1.0 17 Jan 2013

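### The Stage 1 ORR test is a normal-approximation Z-test with an unnamed 90% CI, in groups planned at about six; the usual form of that test does not hold its stated 5% level at several plausible group sizes

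*SAP*

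**What the plan says.** SAP 4.4.1 (Stage 1) states the test: "The ORR will be compared against a fixed level of 10% using one-proportion Z-test". It is done in each of the four treatment groups and overall, each at one-sided 5%. The decision rule is that "statistical significance will be concluded if the lower bound of the 2-sided 90% CI is above 10" percent. Neither document says how the Stage 1 interval is calculated, which variance enters the Z statistic, or whether a continuity correction applies. For Stage 2, by contrast, Protocol 10.1 and 10.3.3 call for exact intervals.

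On group size, Protocol Appendix K describes "Cohort 1: Approximately 12 subjects with intermediate -1, intermediate -2, or high risk MF", and a second cohort of the same size. Each cohort is divided over two schedules, and the division was not randomised: "Subjects will be assigned to a weekly or every four week dosing schedule by the investigator". The Appendix K Simon design gives the null probability "to stop after stage 1 is 53" percent. Protocol 5.1.1 gives the totals as "27 in Stage 1, and up to an additional 84 subjects in Stage 2". No document gives the number in each Stage 1 group.

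On purpose, Appendix K says: "The objective is to demonstrate superiority within each cohort and dose schedule, comparing observed ORR in each arm" with a fixed 10% level. SAP 2.6 nevertheless describes the trial in these words: "This being an open-label non-inferential study".

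**The concern.** With six subjects and a null rate of 10%, 0.6 responders are expected. A normal approximation cannot be relied on there, so the nominal 5% need not be the actual error.

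The SAP also states a test and an interval rule as though they were one procedure. They coincide only if the interval is the one obtained by inverting that same test. Since the interval is not named, the test could say significant while the interval says not significant for the same group.

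At stake is whether the clinical study report calls a Stage 1 group significant on the Stage 1 primary endpoint. Continuation to Stage 2 does not depend on it: Protocol 1.5 and Appendix K required only one response in an arm.

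**Working it through.** **Inputs.** Null rate 0.10 and alternative 0.40 (Appendix K, Statistical Methods). One-sided 5% and a two-sided 90% interval (SAP 4.4.1), so z = 1.645. Planned group size: two cohorts of about 12 over two schedules, 24/4 = 6 if split evenly. Stage 1 total 27 (Protocol 5.1.1), a mean of 27/4 = 6.75.

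**The plan's own figures.** 0.9^6 = 0.531, which is the stated 53%. Take a first stage of 6, stopping at 0 responses, with 20 more subjects and rejection above 5 responses in 26. This gives type I error 0.0339, power 0.938 at 0.40, and expected size 6 + 20 × (1 − 0.531) = 15.4. These match the stated 3.4%, 94% and 15. The cut-off of 5 is inferred, because the design figure is not shown. Six per group is therefore the documents' planning size.

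**Two responders in six (33.3%).**
- Null-variance Z: (0.3333 − 0.10)/√(0.10 × 0.90/6) = 0.2333/0.1225 = 1.905, p = 0.028. Significant.
- Observed-variance Z: 0.2333/√(0.3333 × 0.6667/6) = 0.2333/0.1925 = 1.212, p = 0.113. Not significant.
- Wald lower limit: 0.3333 − 1.645 × 0.1925 = 0.017. Not significant.
- Wilson lower limit: (0.3333 + 0.2255 − 1.645 × √(0.0370 + 0.0188))/1.4509 = 0.117. Significant, as it must be, since Wilson inverts the null-variance Z.
- Clopper-Pearson lower limit: 5th percentile of Beta(2, 5) = 0.063. Not significant.
- Exact p: 1 − 0.9^6 − 6 × 0.1 × 0.9^5 = 1 − 0.5314 − 0.3543 = 0.114.

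At 3/6 all three lower limits exceed 10% (Wald 16.4%, Clopper-Pearson 15.3%, Wilson 22.1%). The exact error of a 3/6 rule is 0.1143 − 15 × 0.01 × 0.6561 = 0.016.

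**Across sizes.** The cut-off c is the smallest count whose lower limit exceeds 10%. Error = P(X ≥ c | n, 0.10); power = P(X ≥ c | n, 0.40). Cells show c, error, power.

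| n | Null-variance Z / Wilson | Wald | Exact / Clopper-Pearson |
|---|---|---|---|
| 4 | 2, 5.2%, 52% | 3, 0.4%, 18% | 3, 0.4%, 18% |
| 5 | 2, 8.1%, 66% | 3, 0.9%, 32% | 3, 0.9%, 32% |
| 6 | 2, 11.4%, 77% | 3, 1.6%, 46% | 3, 1.6%, 46% |
| 7 | 3, 2.6%, 58% | 3, 2.6%, 58% | 3, 2.6%, 58% |
| 8 | 3, 3.8%, 68% | 4, 0.5%, 41% | 3, 3.8%, 68% |
| 9 | 3, 5.3%, 77% | 4, 0.8%, 52% | 4, 0.8%, 52% |
| 10 | 3, 7.0%, 83% | 4, 1.3%, 62% | 4, 1.3%, 62% |
| 27 | 6, 4.7%, 98% | 7, 1.5%, 96% | 6, 4.7%, 98% |

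For n from 2 to 27 the largest exact-test error is 4.7% (at 27).

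**How often the choice would matter in a group of six.** The methods disagree only at exactly two responders. P(X = 2 | n = 6) is 31% at an assumed true rate of 40% and 23% at 50%.

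**The case against.** **Group size.** Six is a planning size, and 27 subjects cannot form four groups of six. At seven all three methods agree, and at eight the usual Z-test agrees with the exact test. A 7/7/7/6 split would leave one group exposed, and only if it had exactly two responders. This stands, and it limits the 11.4% to a group of exactly six. It does not remove the point: the investigator chose the schedule, so unequal groups are possible, and the usual Z-test also exceeds 5% at 4, 5, 9 and 10.

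**The method may be settled already.** A one-proportion Z-test normally uses the null variance, and its matching interval is Wilson. That is a fair reading, but it is the one that breaks the 5% level. Separately, SAP section 1 cites a Stage 1 SAP, Version 2.0, signed before the Stage 1 primary lock. It is not available here and may name the interval. A reader might infer that the interval was left open until results were seen; for this reason the documents do not support that inference.

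**Little is at stake.** Stage 1 is open-label and non-randomised, and SAP 2.6 calls the study non-inferential. That limits the consequence, but SAP 4.4.1 still sets a 5% test and says when significance is concluded.

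**A post hoc change of primary test is intrusive.** This stands as a reason for documenting the change and showing the originally specified result beside it.

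**Conclusion.** The concern holds, at moderate weight. The usual reading of the stated test does not keep its own 5% level at several plausible group sizes (5.2% to 11.4% at n = 4, 5, 6, 9 and 10). Because the interval is unnamed, test and decision rule can also contradict each other. The error rates are exact binomial results at a true ORR of 10%; applying them to this trial needs the realised group sizes, which the documents do not give.

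Three stronger readings are not supported:
- A reader might take 11.4% as the Stage 1 false-positive rate. It belongs to one group size under one method, and no trial-wide rate can be derived without the group sizes.
- A reader might use the 43% overall response at 24 weeks (Protocol 1.5) to judge the overall test at n = 27. It is not a count out of 27: 11/27 = 40.7% and 12/27 = 44.4%. Its denominator is not stated, so it settles nothing either way.
- A reader might think the protocol objective calls for the overall test. Appendix K asks for superiority within each cohort and schedule only; the overall test comes from the SAP.

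The effect is confined to the Stage 1 significance statements.

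**What to change.** In SAP 4.4.1 (Stage 1), replace the one-proportion Z-test with an exact one-sided binomial test against 10%, and name the two-sided 90% interval as Clopper-Pearson. Test and interval then always agree, and each individual test stays at or below 5%. This gives no control across the five tests, and the text should not suggest that it does.

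Because Stage 1 results are known and Version 2.0 of the Stage 1 SAP may already name an interval, record the change and its reason in the clinical study report, and show the originally specified analysis alongside.

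The drafting cost is two phrases, an exact option in the program and a note in the report. The statistical cost depends on what would otherwise be run. Against Wilson, power at a 40% ORR falls from 77% to 46% at n = 6 and from 77% to 52% at n = 9, with no change at 7, 8 or 27; the table shows losses at 4, 5 and 10 too. At those sizes the extra Wilson power comes with an error above 5%. Against Wald, nothing is lost at six, and power rises from 41% to 68% at n = 8 and from 96% to 98% at n = 27.

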### **10.6.1.3. Secondary and exploratory efficacy analyses:**

#### **10.6.1.3.1. Comparison of PRR between treatment arms**

Pairwise comparisons between the three dose groups will be performed using the Cochran-Mantel-Haenszel (general association) statistic in the SAS Freq procedure, to take into account the stratified design, using the following statement:

*tables Stratum\*Treatment\*Response / cmh;*

The Breslow-Day Test for Homogeneity of the Odds Ratios will be examined to detect a potential significant stratum difference in the odds ratios.

Two pairwise comparisons (3 mg/kg versus 0.3 mg/day and 10 mg/kg versus 0.3 mg/day) will be computed with the aim to demonstrating superiority and, consequently, will use an adjusted a two-sided 0.025 level of significance.

The third comparison (10 mg/kg versus 3 mg/kg) is not expected to have enough power to demonstrate any difference with the planned sample size. This comparison is considered exploratory and will be conducted using an unadjusted 0.05 level of significance.

These analyses will be computed on both the FAS (primary analysis set) and PP analysis sets.

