Pentraxin-2 (PTX-2), also known as serum amyloid protein is an endogenous protein that circulates in the bloodstream. Recent discoveries about the biology of tissue repair and fibrosis have elucidated the important role that PTX-2 plays biologically in regulating processes that relate to scar prevention and healing. PTX-2 is an agonist that binds to Fc gamma receptors on monocytes and promotes their differentiation into regulatory macrophages (Mreg), which function to promote epithelial healing and resolution of inflammation and scarring. PTX-2 also prevents the differentiation of monocytes into M2 pro-fibrotic macrophages and fibrocytes, preventing the formation of fibrosis. rhPTX-2 (recombinant human pentraxin-2, RO7490677) is a recombinant version of human pentraxin-2 (rhPTX-2). Similar to endogenous PTX-2, rhPTX-2 circulates as a non-covalent, homo-pentameric glycoprotein. Pre-clinical and clinical data support the investigation of rhPTX-2 in the treatment of fibrotic diseases (Murray et al. 2010; Pilling et al. 2007; Raghu et al. 2018; Verstovsek et al. 2016; Duffield et al. 2010).

Study BO42355 was developed to examine the efficacy and safety of rhPTX-2 in intermediate-1, intermediate-2, and high risk subjects with PMF, post-PV MF, or post-ET MF subjects. More details regarding the study are provided in the Appendix 1, Appendix 2, Appendix 3, and Appendix 4 (Protocol Synopses for the various study stages).

Of note, rhPTX-2 was developed by Promedior and acquired by Roche in 2020. Detailed Statistical Analysis Plans (SAPs) (Stage 1 Version 2.0: 11 April 2019; Stage 2 Version 2.0: 5 March 2018) were prepared by Promedior and signed prior to the respective Stage 1 and Stage 2 primary database lock (DBL) and analyses. This present SAP was prepared by Roche and signed before the final DBL of the Stage 1 and Stage 2 open label extensions (OLEs) of the study. The aim of this SAP is to highlight the analyses that will be performed for the final analysis and reported in a Clinical Study Report (CSR) for both main Stage 1 and Stage 2, and inclusive of their respective OLEs.

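### SAP 4.4.1 (Stage 2) moves the two 0.025-level comparisons against 0.3 mg/kg from stratified CMH to logistic regression, but names no contrast test and no rule for a reference arm without responders

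*SAP*

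**What the plan says.** Protocol 10.6.1.3.1 fixes the test for the dose comparisons: "Pairwise comparisons between the three dose groups will be performed using the Cochran-Mantel-Haenszel (general association) statistic", stratified, with the SAS statement printed. The Stage 2 synopsis agrees. The comparisons of 3 and 10 mg/kg with 0.3 mg/kg are each at two-sided 0.025. Under Protocol 10.3.3 they are run only if at least one arm has first been shown to exceed a 10% response rate.

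SAP 4.4.1 keeps the comparisons and their levels but changes the method: "The BMRR will be analyzed using a logistic regression with bone marrow response at any time during the study (yes/no) as response variable", with treatment group as explanatory variable and adjustment for randomised stratum. On testing it says only: "Pairwise comparisons between the 3 treatment groups will be performed". SAP 4.4.4 adds that "a non-stratified analysis of BMRR will be computing as a sensitivity analysis", again with no model or test named. SAP 4.9 deals with missing data, not with empty cells. The synopsis reprinted in SAP Appendix 3 still specifies CMH, so the SAP carries two methods for the same comparisons.

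The analysis population is subjects "randomized and, who have received at least one administration of the drug", which gives 28 per arm if all 84 are treated.

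SAP section 1 says that detailed Stage 1 and Stage 2 SAPs were "signed prior to the respective Stage 1 and Stage 2 primary database lock (DBL) and analyses". The present SAP was "signed before the final DBL of the Stage 1 and Stage 2 open label extensions" and covers "the analyses that will be performed for the final analysis and reported in a Clinical Study Report".

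Both documents print the low dose in these comparisons as 0.3 mg/day, whereas the arm is 0.3 mg/kg everywhere else. I read it as that arm; the unit must be reconciled.

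**The concern.** Both 0.025-level comparisons share one reference arm, and the protocol expects very few responders in it. A CMH test gives a valid answer when that arm has none. An ordinary logistic regression gives no finite odds ratio in that case, and whether it still gives a usable p-value depends on the contrast test, which the SAP leaves open.

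The comparisons carry weight although they are secondary. Stage 2 has no control arm, and Protocol 1.5 treats a dose response as the evidence of efficacy. The most favourable pattern for the drug, no responders at the lowest dose and many at a higher one, is exactly where the written method is undefined.

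**Working it through.** **Inputs.** Protocol 10.1: response rates 5% (0.3 mg/kg) and 46% (10 mg/kg; at least 46% at 3 mg/kg), 24 per arm, 84 enrolled (84/3 = 28 per arm), two-sided 0.025, stated power 82% for a 39-point difference with a best rate of 46%, that is 46% versus 7%. Protocol 1.4 and 1.5 allow for activity at low doses, so 7% and an assumed 10% are shown as well. Pairs below are for 24 / 28 per arm.

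**The plan's own figure.** Pooled normal approximation, n = 24, 7% versus 46%: the mean rate is 0.265; SE under the null = √(2 × 0.265 × 0.735/24) = 0.1274; SE under the alternative = √((0.07 × 0.93 + 0.46 × 0.54)/24) = 0.1143; z = 2.241. Power = Φ((0.39 − 2.241 × 0.1274)/0.1143) = Φ(0.914) = 0.82. The stated 82% reproduces.

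**How often the reference arm is empty.** Expected responders at 5%: 24 × 0.05 = 1.2 and 28 × 0.05 = 1.4. P(none) = (1 − p)^n:

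| True rate at 0.3 mg/kg | n = 24 | n = 28 |
|---|---|---|
| 5% | 0.292 | 0.238 |
| 7% | 0.175 | 0.131 |
| 10% (assumed) | 0.080 | 0.052 |

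**What the model gives then.** With no responders in the reference arm, its fitted log-odds run to minus infinity and both log odds ratios to plus infinity, whichever test is used. For 0/24 versus 11/24, an ordinary fit stops at a log odds ratio of about 23 with a standard error of about 16,000 and Wald p = 0.999; Mantel-Haenszel gives p = 0.0002.

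**Power by contrast test.** Full enumeration of two binomial arms without strata, two-sided 0.025, against 46%:

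| Low-dose rate | Wald | Mantel-Haenszel | Likelihood ratio |
|---|---|---|---|
| 5% | 0.540 / 0.682 | 0.914 / 0.948 | 0.915 / 0.958 |
| 7% | 0.590 / 0.741 | 0.857 / 0.903 | 0.858 / 0.920 |
| 10% | 0.584 / 0.729 | 0.754 / 0.814 | 0.754 / 0.839 |

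At 5%, the share of the Wald shortfall against Mantel-Haenszel that comes from trials with no low-dose responders is 0.78 / 0.89. A simulation of the three-arm model with stratum terms (3,000 runs; strata of about 40/30/30%, an assumption) agrees at 5%: Wald 0.56 / 0.70, CMH 0.91 / 0.95, likelihood ratio 0.92 / 0.96.

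**Type-one error of the alternatives.** At a common 10% rate and ignoring the gate, the likelihood-ratio test rejects with probability 0.038 / 0.038 and Mantel-Haenszel with 0.017 / 0.021. The gate of Protocol 10.3.3, with an exact 97.5% interval, needs at least 7/24 or 8/28 responders; at a true 10%, one arm reaches that with probability 0.0075 / 0.005. Enumerating three arms with the gate applied to 3 and 10 mg/kg, the error per comparison is 0.0025 / 0.0016 for likelihood ratio and 0.0024 / 0.0015 for Mantel-Haenszel. Over common rates from 5% to 46%, the gated likelihood-ratio error peaks at 0.029 / 0.025.

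**Example, 0/28 versus 13/28, unstratified.** Mantel-Haenszel χ² = 55 × (28 × 13)² / (28 × 28 × 13 × 43) = 16.6, p = 0.00005. Risk difference 13/28 = 46%, 97.5% score interval 27% to 67%. The ordinary odds ratio is infinite; the Firth odds ratio is 50, 97.5% profile interval 4.6 to about 21,000.

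**The case against.** The strongest reply is that this is a modest gap in a secondary comparison. Protocol 10.3.1 allows changes of method if they are documented in the study report. Stratum adjustment is kept. The comparison of each higher dose with 10% does not use the model. Each arm's rate is reported with a 95% interval, so 0/28 against 13/28 would be visible. The protocol's CMH plan named no effect estimate either. SAP 2.6 even calls the study non-inferential, although that sits badly with the superiority aim in SAP 4.4.1. The earlier Stage 2 SAP may name the test or may itself have introduced the logistic model. All of this stands and limits the weight of the point. None of it supplies the missing test or the missing rule in this SAP.

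Three stronger readings are tempting, and the documents do not support them.

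- A reader might infer that the comparisons have only 54% power. That requires Wald contrasts, which the SAP does not state; a likelihood-ratio test on the same model loses nothing against CMH.
- A reader might infer from the 0.038 that the likelihood-ratio test is unsafe and CMH is the only acceptable choice. Under the protocol's gate the error at that rate is about 0.002, almost the same as Mantel-Haenszel. The 0.038 applies only if the gate is dropped; SAP 4.4.1 does not restate it.
- A reader might infer that the reported result is affected. This SAP postdates the Stage 2 primary lock, so the low-dose count may already have been known, and the documents do not give it.

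**Conclusion.** The point holds as a specification gap that should be fixed. The SAP changes the test for the two multiplicity-adjusted dose comparisons, leaves the contrast test unnamed, and is silent on a case with probability 0.29 (24 per arm) or 0.24 (28 per arm) at the protocol's own 5%. The probability falls to 0.18 / 0.13 at 7% and 0.08 / 0.05 at an assumed 10%. In that case the stated model yields no finite odds ratio for either comparison. This conclusion depends on the low-dose rate but not on the test chosen.

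The power loss is conditional on Wald contrasts. The enumeration ignores strata, and the simulation rests on assumed stratum sizes with a constant rate across them. All figures describe the method as written, at design-stage rates.

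**What to change.** In SAP 4.4.1 (Stage 2), use the protocol's CMH test, stratified by randomised stratum, for the two 0.025-level comparisons. Report a stratified risk difference with a 97.5% score interval, which stays finite when an arm has no responders. Keep the logistic model as supportive, with Firth penalisation and profile-likelihood intervals if an odds ratio is reported.

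A sound alternative is to keep the logistic model as the main analysis, name a likelihood-ratio or Firth penalised test instead of Wald, and state what is reported when an arm has no responders. In that case, say whether the gate of Protocol 10.3.3 still applies; if it does not, state that the unconditional likelihood-ratio error reaches 0.038 at a common 10% rate.

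Either way, record the reason for any departure from CMH and reconcile it with the synopsis in SAP Appendix 3.

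The cost is two or three sentences and one extra procedure call, with no new data. CMH has two drawbacks: it gives no model-based odds ratio, and it slightly exceeds its level in some cases (0.029 at a common 46% with 24 per arm).
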